13.0 Study Timelines*

13.1 Describe the anticipated duration needed to enroll all study subjects.

Response: Approximately 3 months will be needed for enrollment.

13.2 Describe the duration of an individual subject's participation in the study. Include length of study visits, and overall study follow-up time.

Response: Study duration is approximately 8 weeks and includes 6 visits if the screening is on the same day as visit 1. Each visit is approximately 45 mins to 1.5 hour.

13.3 Describe the estimated duration for the investigators to complete this study (i.e. all data is collected and all analyses have been completed).

Response: 6 months including data analysis.

14.0 Setting

14.1 Describe all facilities/sites where you will be conducting research procedures. Include a description of the security and privacy of the facilities (e.g. locked facility, limited access, privacy barriers). Facility, department, and type of room are relevant. Do not abbreviate facility names.

NOTE: Examples of acceptable response may be: "A classroom setting in the Department of Psychology equipped with a computer with relevant survey administration software," "The angiogram suite at Buffalo General Medical Center, a fully accredited tertiary care institution within New York State with badge access," or, "Community Center meeting hall."

Response: Center for Dental Studies, University at Buffalo School of Dental Medicine. The Center for Dental Studies is a dedicated space for clinical dental investigations.

14.2 For research conducted outside of UB and its affiliates, describe:

- Site-specific regulations or customs affecting the research
- Local scientific and ethical review structure

NOTE: This question is referring to UB affiliated research taking place outside UB, i.e. research conducted in the community, school-based research, international research, etc. It is not referring to multi-site research. UB affiliated institutions include Kaleida Health, ECMC, and Roswell Park Cancer Institute.

Response:

N/A: This study is not conducted outside of UB or its affiliates.

15.0 Community-Based Participatory Research

15.1 Describe involvement of the community in the design and conduct of the research.

NOTE: Community-Based Participatory Research (CBPR) is a collaborative approach to research that equitably involves all partners in the research process

and recognizes the unique strengths that each brings. CBPR begins with a research topic of importance to the community, has the aim of combining knowledge with action and achieving social change to improve health outcomes and eliminate health disparities.

Response:

N/A: This study does not utilize CBPR.

15.2 Describe the composition and involvement of a community advisory board.

Response:

N/A: This study does not have a community advisory board.

16.0 Resources and Qualifications

*16.1 Describe the qualifications (e.g., education, training, experience, expertise, or certifications) of the Principal Investigator **and** staff to perform the research. When applicable describe their knowledge of the local study sites, culture, and society. Provide enough information to convince the IRB that you have qualified staff for the proposed research.*

NOTE: If you specify a person by name, a change to that person will require prior approval by the IRB. If you specify a person by role (e.g., coordinator, research assistant, co-investigator, or pharmacist), a change to that person will not usually require prior approval by the IRB, provided that the person meets the qualifications described to fulfill their roles.

Response: The principal investigator (PI) has extensive experience in clinical dental research. The PI has conducted over 60 clinical trials spanning 45 years. In addition, the support staffs in the study have undergone professional training (including dentistry and dental hygiene) to render dental examinations and care and have collaborated with the PI on multiple projects. The clinical coordinator has been associated with the Center for over 20 years.

Describe other resources available to conduct the research.

16.2 Describe the time and effort that the Principal Investigator and research staff will devote to conducting and completing the research.

NOTE: Examples include the percentage of Full Time Equivalents (FTE), hours per week. The question will elicit whether there are appropriate resources to conduct the research.

Response: PI-2%, Study Coordinator 10%, Study Examiner 16%

16.3 Describe the availability of medical or psychological resources that subjects might need as a result of anticipated consequences of the human research, if applicable.

NOTE: One example includes: on-call availability of a counselor or psychologist for a study that screens subjects for depression.

Response: If an adverse event occurs, the subject may be scheduled for a follow-up or under the direction of the Principal Investigator referred to a physician or dentist for treatment. Serious Adverse Events will be followed to the extent of resolution possible. Also, Subjects enrolled in the study may elect to withdraw at any time for any reason.

16.4 Describe your process to ensure that all persons assisting with the research are adequately informed about the protocol, the research procedures, and their duties and functions.

Response: A pre-study briefing will be conducted by the PI with the staff of the Center for Dental Studies to ensure that the study staff understands the design and methodology of the study. Support staff will be encouraged to seek help from the PI if they are concerns/questions related to the study procedures.

17.0 Other Approvals

17.1 Describe any approvals that will be obtained prior to commencing the research (e.g., school, external site, funding agency, laboratory, radiation safety, or biosafety).

Response:

N/A: This study does not require any other approvals.

18.0 Provisions to Protect the Privacy Interests of Subjects

18.1 Describe how you will protect subjects' privacy interests during the course of this research.

NOTE: Privacy refers to an individual's right to control access to him or herself. Privacy applies to the person. Confidentiality refers to how data collected about individuals for the research will be protected by the researcher from release. Confidentiality applies to the data.

Examples of appropriate responses include: "participant only meets with a study coordinator in a classroom setting where no one can overhear", or "the participant is reminded that they are free to refuse to answer any questions that they do not feel comfortable answering."

Response: The clinical dental research center is a dedicated space equipped for private discussions with the patient. This space will be used to collect personal data as it pertains to the study as well as for obtaining informed consent

18.2 *Indicate how the research team is permitted to access any sources of information about the subjects.*

*NOTE: Examples of appropriate responses include: school permission for review of records, consent of the subject, HIPAA waiver. This question **does apply** to records reviews.*

Response: The research team will collect data, by consent of the subject, as it relates to this study in order to determine if inclusion and exclusion criteria are met. All subject identification will be coded so that the subject's identity is protected. Further, clinical data will be used to assess the efficacy and safety of the mouthrinse. Additional sources of data from other healthcare providers will not be accessed.

All subjects will sign and be given a copy of the informed consent agreement. The Principal Investigator will maintain the original informed-consent document in the case report folder.

Prior to commencing the study, the Principal Investigator will obtain approval from the Institutional Review Board (IRB) in Compliance with Federal Regulations (21 CFR 56). The IRB will be consulted on the required information for review. Variations or changes in the protocol will not be implemented until approved by the Institutional Review Board.

19.0 Data Management and Analysis*

19.1 *Describe the data analysis plan, including any statistical procedures. This section applies to both quantitative and qualitative analysis.*

Response: This is a randomized double-blind placebo controlled crossover study comparing the HYDRAL Oral rinse to Biotene rinse, and HYDRAL Oral rinse to placebo. A one-week wash-out period will be adopted between phases to eliminate any possible carry-over effect of a treatment from previous phase. The primary endpoint is a reduction of dry mouth symptom in VAS (0-10 scale). To control for the Type I error rate of incorrectly rejecting the null hypothesis, a two-sided significance level of 0.025 will be used. A power analysis for a crossover study estimated that with 80% power, 33 subjects will be required to detect a minimal difference in mean VAS of 0.8. To account for withdrawal and other factors (e.g. failed measurement), a total of 39 subjects will be recruited and randomized into the study.

Descriptive statistics for all subjects will be performed for background and demographic variables. Continuous variables are expressed as frequencies (n), mean +/- SD and categorical variables are expressed as frequencies (n) and percentages (%). To evaluate the primary end point, an Analysis of variance will be applied to examine the possible residual or carryover effects of treatments. If no residual effect is found, paired t test or Wilcoxon sign-rank test where appropriate, will be used to compare treatments; however, if residual effect is significant, a mixed model (with unstructured covariance matrix) will be performed with treatment, period,

and interaction of treatment and period as fixed effects to account for treatment, period, and carryover effect. For categorical variables, percent or proportion of subjects will be calculated and a Chi-square test or McNemar test will be used. All statistical tests will be conducted using SAS version 9 (SAS Institute Inc. Cary, NC).

19.2 *If applicable, provide a power analysis.*

NOTE: This may not apply to certain types of studies, including chart/records reviews, survey studies, or observational studies. This question is asked to elicit whether the investigator has an adequate sample size to achieve the study objectives and justify a conclusion.

Response: The number of subjects needed for this study with adequate power is based on a power analysis of 0.8.

19.3 *Describe any procedures that will be used for quality control of collected data.*

Response: The PI and the clinical study member are calibrated in the collection of data required for this study.

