1.0 Study Summary

Study Title	Clinical evaluation of the efficacy of an intra oral rinse for patients with xerostomia
Study Design	Randomized, double –blind, placebo controlled cross over study
Primary Objective	
1. To evaluate patients’ perception of efficacy of a new currently marketed mouth rinse (HYDRAL) for xerostomia compared to a placebo mouth rinse (negative control) and another currently marketed mouthrinse (Biotene) in reducing the symptoms of xerostomia.2. To determine the efficacies on dry mouth relief and on the patient’s Quality of Life (QoL) at the beginning and end of the study.
Secondary Objective(s)	
1. To objectively evaluate the improvement of dry mouth symptoms by HYDRAL compared to the placebo and Biotene.2. To evaluate the safety of the test mouthrinse on teeth and oral soft tissues.3. To evaluate the patient’s preferences relative to the test mouthrinses.
Research Intervention(s)/ Investigational Agent(s)	Mouth rinse (HYDRAL)
IND/IDE #	N.A

Study Population	Adults males and females
Sample Size	39
Study Duration for individual participants	8 weeks
Study Specific Abbreviations/ Definitions	

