2.0 Objectives*

2.1 Describe the purpose, specific aims, or objectives of this research.

Response: The objectives of this randomized double -blind placebo controlled cross over study are:

- 1) To evaluate patients' perception of efficacy of a new mouth rinse (HYDRAL) for xerostomia compared to a placebo mouth rinse (negative control) and another mouthrinse (Biotene) in reducing the symptoms of xerostomia.
- 2) To determine the efficacies on dry mouth relief and on the patient's Quality of Life (QoL) at the beginning and end of the study.
- 3) To objectively evaluate the improvement of dry mouth symptoms by HYDRAL compared to the placebo and Biotene.
- 4) To evaluate the safety of the test mouthrinse on teeth and oral soft tissues.
- 5) To evaluate the patient's preferences relative to the test mouthrinses.

2.2 State the hypotheses to be tested, if applicable.

NOTE: A hypothesis is a specific, testable prediction about what you expect to happen in your study that corresponds with your above listed objectives.

Response:

- 1) HYDRAL performs as well as or better than Biotene in reduction of the symptoms. HYDRAL performs better than the placebo rinse in reduction of the symptoms.
- 2) HYDRAL improves patient's quality of life as well as or better than Biotene. HYDRAL performs better than the placebo rinse in improvement of patient's Quality of Life (QoL)

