3.0 Scientific Endpoints*

2.1 Describe the scientific endpoint(s), the main result or occurrence under study.

NOTE: Scientific endpoints are outcomes defined before the study begins to determine whether the objectives of the study have been met and to draw conclusions from the data.

*Include primary and secondary endpoints. Some example endpoints are: reduction of symptoms, improvement in quality of life, or survival. Your response should **not** be a date.*

Response: The primary endpoint is a reduction of dry mouth symptoms

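### Section 19.1 tests the two VAS comparisons at a fixed two-sided 0.025; Holm at overall 0.05 has the same 5% bound and is never less powerful

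*Combined protocol and SAP*

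**What the plan says.** Section 19.1 describes the trial as "comparing the HYDRAL Oral rinse to Biotene rinse, and HYDRAL Oral rinse to placebo", with reduction in dry mouth on a 0–10 VAS as the primary endpoint. The error rule is one sentence: "To control for the Type I error rate of incorrectly rejecting the null hypothesis, a two-sided significance level of 0.025 will be used". It states neither an overall level nor a split between the comparisons, and no stepwise rule appears anywhere in the document.

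The sample size statement is "with 80% power, 33 subjects will be required to detect a minimal difference in mean VAS of 0.8", raised to 39 randomised to allow for losses. No standard deviation is given. If no carryover is found, "paired t test or Wilcoxon sign-rank test where appropriate, will be used to compare treatments"; otherwise a mixed model with treatment, period and their interaction is fitted.

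Section 2.2 expects superiority over placebo. For the active comparator it says "HYDRAL performs as well as or better than Biotene in reduction of the symptoms", without a margin.

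**The concern.** With two comparisons and a sentence about Type I error control, 0.025 is most naturally 0.05 divided by two. A fixed split holds the second comparison to 0.025 even after the first has succeeded, which the 5% bound does not require. If HYDRAL is truly better than both comparators, the fixed rule therefore misses one of the two differences more often than it has to. What is at stake is power for the second comparison, usually the one with Biotene. The validity of the plan is not in question.

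**Working it through.** **Inputs from section 19.1:** two comparisons; two-sided 0.025; 80% power; n = 33; difference 0.8; 39 randomised.

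**Assumptions, not in the documents:**
- The correlation between the two paired differences is 0.5. This follows if the three periods have equal variances and covariances, because both differences share the HYDRAL period: covariance σ²(1−ρ) over variance 2σ²(1−ρ) = 0.5. The range 0.3 to 0.7 is also shown.
- The Biotene comparison is a two-sided test of difference, since no margin is stated.

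**Step 1. The plan's own figure.** Without an SD, n = 33 can only be back-solved. From n = (SD × (z₀.₉₈₇₅ + z₀.₈₀)/0.8)², with z₀.₉₈₇₅ + z₀.₈₀ = 3.083:

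SD = 0.8 × √33 / 3.083 = 1.49 (normal approximation).

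The exact paired t calculation gives 1.43, which is used below. Other SDs would need a different n by the paired t test: 24 at SD 1.2, 41 at 1.6, 51 at 1.8.

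**Step 2. Error bound.**
- Fixed rule: 0.025 + 0.025 = 0.05.
- Holm, both differences zero: a false claim needs the smaller p-value to be at most 0.025. This is the same event as under the fixed rule, so the same bound holds.
- Holm, only one difference zero: a false claim needs that comparison's p-value to be at most 0.05, so the error is at most 0.05.

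Neither argument uses the SD, the correlation or the type of test.

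**Step 3. Where the gain comes from.** The rules differ only when one p-value is at most 0.025 and the other lies between 0.025 and 0.05. Holm then claims both and the fixed rule claims one. The chance of at least one claim is therefore identical. At n = 33 a single test of a 0.8 difference has 80.0% power at 0.025 and 87.5% at 0.05.

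**Step 4. Size.** Simulated paired t trials, SD 1.43, correlation 0.5; percentages, fixed → Holm.

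| n | True difference, placebo / Biotene | Placebo claimed | Biotene claimed | Both claimed | At least one (same for both rules) |
|---|---|---|---|---|---|
| 33 | 0.8 / 0.8 | 80 → 85 | 80 → 85 | 69 → 79 | 92 |
| 33 | 0.8 / 0.6 | 80 → 82 | 53 → 62 | 48 → 60 | 85 |
| 33 | 0.8 / 0.4 | 80 → 81 | 24 → 33 | 23 → 33 | 81 |
| 33 | 0.8 / 0.2 | 80 → 80 | 7 → 12 | 7 → 12 | 80 |
| 33 | 0.8 / 0 | 80.0 → 80.2 | 2.5 → 4.3 (false) | – | 81 |
| 39 | 0.8 / 0.8 | 87 → 91 | 87 → 91 | 79 → 87 | 95 |
| 39 | 0.8 / 0.4 | 87 → 88 | 29 → 39 | 28 → 39 | 88 |

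With both differences zero, family-wise error is 4.7% under both rules. The normal approximation gives 4.2% instead of 4.3% in the equality row.

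**Step 5. Sensitivity to correlation (n = 33).** At 0.3 and 0.7, both claimed at 0.8 / 0.8 goes from 66% to 77% and from 71% to 80%. Biotene power at 0.8 / 0.4 goes from 24% to 33% and from 24% to 34%. The false-claim rate under equality is 4.4% and 4.1%.

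**Step 6. Intervals.** The 97.5% half-width at n = 33 is 2.352 × 1.43/√33 = 0.59 VAS points; at 95% it is 2.037 × 1.43/√33 = 0.51. By Step 3, the gain in both claimed is also the share of trials in which Holm claims a difference whose 97.5% interval includes zero. At 0.8 / 0.8 that is about 10% (9% by the normal approximation).

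**The case against.** The strongest reply is that nothing is broken. The fixed split is valid and matches simple simultaneous 97.5% intervals. The as-good-as-Biotene question must rest on an interval, because section 2.2 gives no margin. This stands, and it is why the point is an improvement only.

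Four further objections carry weight:
- The 0.8 / 0.8 case implies that Biotene works no better than placebo. The rows with a smaller Biotene difference are more plausible for a marketed comparator. At 0.4 or 0.2, power against Biotene stays low under either rule.
- Section 22.3 replaces withdrawals, so evaluable numbers may be near 39. There the fixed rule already shows both in 79% of trials at 0.8 / 0.8, as often as Holm does at 33. Holm still adds about 8 points at 39.
- Holm is not the only alternative. Testing placebo first at 0.05, then Biotene at 0.05, also keeps the bound and gives about 87.5% power against placebo. It makes the Biotene claim depend on the placebo result: at 0.8 / 0.8, Biotene is claimed in about 80% of trials, against 85% under Holm. The sponsor may prefer it, but Holm's advantage over the stated rule remains.
- In the mixed-model branch, the treatment-by-period interaction leaves no single p-value per comparison until a contrast is named. The fix covers this.

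A reader might infer that family-wise error is inflated because section 1.0 lists quality of life under the primary objective ("Quality of Life (QoL) at the beginning and end of the study") and section 2.2 attaches hypotheses to it ("quality of life as well as or better than Biotene"). The documents do not support that. Section 3.0 says "The primary endpoint is a reduction of dry mouth symptoms", and 19.1 names only VAS as primary. Whether quality of life is confirmatory is a separate clarification for the sponsor.

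**Conclusion.** The point holds as an efficiency improvement. That Holm claims at least as much as the fixed rule, under the same 5% bound, does not depend on any assumed figure. It does rest on reading 0.025 as half of 0.05, which 19.1 does not say in words.

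The size depends on the back-solved SD and the assumed correlation. At n = 33 and a placebo difference of 0.8, power against Biotene gains about 9 points when the Biotene difference is 0.6 or 0.4. Among the cases shown, the chance of showing both gains most at 0.8 / 0.6, about 12 points, and about 10 points at 0.8 / 0.8.

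Three stronger readings should be resisted:
- The plan's error rule is not wrong.
- The chance of at least one success does not rise.
- Holm supplies no non-inferiority test. If HYDRAL merely equals Biotene, it brings 0.2 points against placebo and a higher, still bounded, rate of false differences.

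**What to change.** In 19.1, before unblinding:
- State that the overall two-sided alpha is 0.05 over the two VAS comparisons.
- Test the smaller p-value at 0.025. If it is significant, test the other at 0.05; otherwise stop.
- If the mixed model is used, apply the rule to the p-values of the two named treatment contrasts, HYDRAL minus Biotene and HYDRAL minus placebo.
- Keep the sample size of 39 and its 0.025 basis.
- Report 97.5% intervals for both comparisons, and flag any claim that rests on the second step.

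The cost is a few sentences and the IRB approval that section 18.2 requires for protocol changes, with no extra subjects or data. The downside is that tests and simple simultaneous intervals no longer always agree, which the flag makes visible. Keeping the fixed 0.025 remains valid at the lower power shown; in that case 19.1 should still say that it is 0.05 divided over two comparisons.

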Response: If patients withdraw or are withdrawn from the study, the reason for withdrawal will be retained and de-identified in the final report of the study. Subjects who withdraw prior to last visit will be replaced with another subject and given the same treatment. To maintain the double-blind, the treatment will be determined by a third party who provided the randomization codes.

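### Section 19.1 plans no covariate adjustment for the VAS already taken at the start of each period; adding it in one prespecified model is a cheap, likely gain in precision

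*Combined protocol and SAP*

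**What the plan says.** The VAS question is put before and after each two-week use (Section 8.1). It is scored at Visits 1, 3 and 5, when each product starts, and at Visits 2, 4 and 6, when it ends (Section 12.1; Study Schedule table in Section 12.2).

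Section 19.1 defines the outcome thus: "The primary endpoint is a reduction of dry mouth symptom in VAS (0-10 scale". Power is stated on another wording: "33 subjects will be required to detect a minimal difference in mean VAS of 0.8", at 80% power and two-sided 0.025. Allowing for losses, "a total of 39 subjects will be recruited and randomized into the study".

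The analysis has two steps. First, "an Analysis of variance will be applied to examine the possible residual or carryover effects of treatments". Then "If no residual effect is found, paired t test or Wilcoxon sign-rank test where appropriate, will be used to compare treatments". Where the first step does find carry-over, the fallback is this: "a mixed model (with unstructured covariance matrix) will be performed with treatment, period". Its third fixed effect is the treatment-by-period term, meant to capture carry-over. Neither branch has the period-start VAS as a covariate.

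**The concern.** In a crossover, stable differences between subjects cancel. What remains is variation within a subject from period to period, and the VAS at the start of a period may predict part of it. Where it does, a comparison that leaves it out has a wider standard error than it needs.

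Section 19.1 also does not settle which quantity is compared. A reduction suggests change from the period's start; a difference in mean VAS suggests the end score. The end score makes no use of the baseline. The change score uses it only by subtraction, which fixes its slope at 1 whether or not the data support that. A fitted slope avoids having to choose. At stake is precision, not validity.

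**Working it through.** **Inputs.** From Section 19.1: difference 0.8, two-sided 0.025, power 80%, 33 evaluable, 39 randomised. Not in the documents, so assumed: the SD of the within-subject product difference; r, the correlation between the product difference in period-start VAS and the product difference in end VAS; and k, the SD of the baseline difference divided by the SD of the end difference. Note that r is taken after subject effects cancel. It is not the ordinary baseline-to-end correlation: with equal between- and within-subject variance and no within-subject correlation, the ordinary correlation is 0.5 while r is 0.

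**Step 1: the plan's 33.** With no SD stated, 33 can only be solved backwards. By the exact paired t test (noncentral t), 33 is the required number for an SD of the difference of about 1.41 to 1.43. At 1.43 the noncentrality is 0.8 × √33 / 1.43 = 3.21 and power is 80.1%. At 39 it is 0.8 × √39 / 1.43 = 3.49 and power is 87.2%.

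**Step 2: variances.** Set the variance of the end-score difference to 1.
- End score: 1
- Change score: 1 + k² − 2rk
- Adjusted: 1 − r², before the small cost of estimating the slope

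With k = 1 the change-score variance is 2(1 − r), so adjusted over change is (1 + r)/2. With k = 0.5 and r = 0.5 the change-score variance is 1 + 0.25 − 0.5 = 0.75 and the adjusted variance is 1 − 0.25 = 0.75. They tie, and the cost of the slope makes adjustment slightly worse.

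**Step 3: power of the adjusted comparison.** This is the test of the intercept in a regression of end difference on baseline difference, by simulation. In each row the unadjusted test of the quantity that was powered has 80% at 33 and 87% at 39.

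| 33 was set for | Evaluable | r = 0 | 0.25 | 0.5 | 0.7 |
|---|---|---|---|---|---|
| End score | 33 | 79% | 81% | 90% | 98% |
| End score | 39 | 86% | 88% | 94.5% | 99% |
| Change score, k = 1 | 33 | 98% | 94.5% | 90% | 85% |
| Change score, k = 1 | 39 | 99% | 97.5% | 94.5% | 91% |
| Change score, k = 0.5 | 33 | 87% | 81% | 79% | 82% |
| Change score, k = 0.5 | 39 | 93% | 89% | 86% | 89% |

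Against the end score, break-even is near r = 0.2. The 98% at r = 0 in the third row is not a gain from adjustment: the plain end score also has 98% there, and the gain comes from not subtracting the baseline.

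**Step 4: the full three-period model.** Simulated with six sequences, subject, period and treatment effects, and 33 set for end scores with k = 1, the adjusted model at 33 has 81, 83, 92 and 98% against about 82% unadjusted. The pattern is that of the first row.

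**Step 5: carry-over into the next baseline.** Suppose two products differ by c VAS points in what they leave in the next period's baseline, and this is gone by the end of that period. With six balanced sequences (not stated in the documents), each product directly follows a given other product in 2 of 6 sequences, so mean baselines differ by c/3. The adjusted contrast then shifts by slope × c/3 towards the longer-lasting product. For c = 0.5 and slope 0.5 that is 0.5 × 0.5 / 3 = 0.08. The change score shifts by 0.5 / 3 = 0.17, and the end score by about 0.

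**The case against.** The strongest reply is that the planned test is valid, the gain rests on a correlation nobody has stated, and the remedy brings a route to bias that an end-of-period paired test does not have. Much of this stands. Below r of about 0.2 there is nothing to gain over the end score. Against a change score with a small baseline SD, adjustment can lose about 1.5 points. The Visit 3 and 5 baselines follow another product, and a shift of 0.08 is a tenth of the 0.8 target. The Visit 1 baseline may be the screening score, selected at 4 or more (Sections 8.1 and 12.1), which could weaken its correlation with the end score. These points limit the claim but do not remove it. For a slope of 1 or less the shift is no larger than a change score's, and the paired end-of-period test can stay as a check.

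A reader might infer three stronger things that the documents do not support:
- That Section 19.1 ignores the baseline altogether. The stated reduction may be a change from period start, which uses it by subtraction.
- That the trial is underpowered. An unadjusted power near 48% (change score at r = 0 with k = 1, when 33 was set for end scores) needs the analysed quantity to differ from the powered one, and the text does not show that it does.
- That 80% to 90% is the expected gain. It holds at r = 0.5 against the end score, or against a change score with equal variances, and 0.5 is an assumption.

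**Conclusion.** The point holds as a cheap improvement. The starting VAS is collected in every period and no planned analysis adjusts for it. For r from 0 to 0.7 at 33 evaluable subjects, adjustment moves power from 80% to between 79 and 98% if 33 was set for end scores. If it was set for change scores, the range is 85 to 98% with equal variances and 79 to 87% with half the baseline SD. The worst loss in the cases examined is about 1.5 points; the gain is about 10 points at r = 0.5 in the first two settings. All of this rests on an SD solved backwards from 33, on assumed r and k, and on both being alike across periods. The paired test is not invalid and 33 is not shown to be wrong. Stating the SD behind 33 is a separate reporting matter.

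**What to change.** In Section 19.1:

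1. Make the primary analysis one mixed model of end-of-period VAS (Visits 2, 4, 6) with treatment, period, that period's pre-treatment VAS (Visits 1, 3, 5) and the subject's mean pre-treatment VAS. Take the two HYDRAL contrasts at the planned two-sided 0.025. With the period-start VAS in the model, the contrast is the same for the end score and for the reduction, so the stated endpoint is kept.
2. State that this model is primary whatever the carry-over ANOVA shows, and keep that ANOVA as descriptive only.
3. Keep the paired t or Wilcoxon test of end-of-period VAS as a sensitivity analysis, because it is free of the baseline carry-over shift.

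The cost is a few lines of wording and two covariates, settled before unblinding, with no new data, visits or subjects. The price in performance is about 1 to 1.5 power points if r is near 0, or against a change score with a small baseline SD, plus the possible shift of slope × c/3.
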